4.1. Inclusion Criteria

- 1) Men or post-menopausal women.
- 2) Age= 60+ years.
- 3) All ethnic groups.
- 4) BMI between 30-38 kg/m² (BMI >29.5 will be rounded up).
- 5) Diagnosis of pre-diabetes (HbA1c 5.7-6.4%).
- 6) Stable body weight (±3% for ≥3 months).
- 7) Willing to adhere to medication regimen for three months.
- 8) Montreal Cognitive Assessment score ≥21.

Version: 2.4 10-29-2020

4.2. Exclusion Criteria

- 1) Diagnosis of diabetes based on ADA criteria
- 2) Impaired renal function with eGFR < 45 mL/min/1.73m². Unstable or rapidly progressing renal failure.
- 3) Impaired liver function with labs ≥3 times upper limits of normal range
- 4) Abnormal hematocrit with lower limits of ≤30%
- 5) Abnormal triglycerides with upper limits ≥600 mg/dL
- 6) Abnormal TSH values ≤0.3 and ≥10
- 7) Urinalysis results with >5-10 white blood cell count
- 8) Current medications known to affect glucose and lipid homeostasis (anti-diabetes medications, glucocorticoids, atypical antipsychotics, anti-transplant rejection medications, anti-retrovirals).
- 9) Current treatment with anticoagulants (warfarin). Aspirin (up to 325 mg) and clopidogrel will be permitted if these can be held for seven days prior to the biopsies.
- 10) History of recent cardiovascular event in the last 6 months or Heart Failure (New York Heart Classification greater than class III-IV; recent EKG changes that suggest active heart disease
- 11) Poorly controlled blood pressure (systolic BP>180, diastolic BP>100 mmHg)
- 12) Active inflammatory, autoimmune, infectious, hepatic, gastrointestinal, malignant, and uncontrolled psychiatric disease (Subjects with depression, anxiety, PTSD, etc. can enroll if controlled and on stable medication)
- 13) Blood donation within 2 months prior to enrollment
- 14) History of frequent UTI

4.3. Subject Recruitment and Screening

We will screen up to 100 potentially eligible candidates to achieve the target enrollment of 20 completes. More candidates will be screened if attrition (est. 20%) requires it.

Subjects will be recruited by advertisement, web-based notices including social media, digital outlets, referrals from the Barshop Clinical Research Call Center, flyers distributed and posted in senior centers, private geriatric offices, and through the outpatient clinics of UT Health San Antonio/UT Medicine Physicians, and University Health System (UHS).

Screening will be performed during Visits 1 and 2.

4.4. Early Withdrawal of Subjects

4.4.1. When and How to Withdraw Subjects

Subjects have the right to withdraw fully or partially from the study at any time and for any reason without prejudice to his or her future medical care by the physician or at the institution.

Withdrawal of full consent for a study means that the subject does not wish to receive further investigational treatment and does not wish to or is unable to continue further study participation including any follow-up in person, by phone, through third parties including relatives or friends, via discussion with other treating physicians, and by use of medical records; subject data up to withdrawal of full consent will be included in the

Version: 2.4_10-29-2020

analysis of the study. Any subject may withdraw full consent to participate in the study at any time during the study. The Sponsor Investigator or sub-investigator will discuss with the subject appropriate procedures for withdrawal from the study.

4.4.2. Data Collection and Follow-up for Withdrawn Subjects

If subjects are withdrawn prematurely from the study, appropriately designated research staff will make efforts to collect at least survival data throughout the protocol defined follow-up period for that subject.

Investigator will consult with Study Statistician with regard to any incomplete data set as compared to the full data set that fully supports the analysis. If a subject withdraws consent to participate in the study, attempts will be made to obtain permission to record survival data up to the protocol-described end of subject follow-up period.

Investigator and designated research staff make it a high priority to obtain survival data on all subjects lost to follow up. Lost to follow up will be defined as a subject missing 2 or more consecutive visits, not answering or responding to 3 follow up phone calls to subject or emergency contacts, or returned receipt of 1 certified letter.

5. Study Drug

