3.3. Study Endpoints

Primary outcome: The primary endpoint for this study is a reduction in urine AGE-RAGE measurements as a result of dapagliflozin treatment. We will be assessing AGE-RAGE in all subjects at baseline and after intervention

Secondary outcomes: Mitochondrial function: This measurement will assess changes in muscle mitochondrial respiration after dapagliflozin treatment. Measurements will occur using muscle samples obtained at baseline and after intervention.

Insulin Sensitivity: This measurement will be obtained before and after the intervention using the HOMA-IR index derived from the fasting insulin and glucose concentrations.

Oxidative Stress: This measurement will be assessed in muscle samples obtained at baseline and after intervention.

Healthspan Measurements: These assessments will include grip strength, isometric knee extension, 6-minute walking distance, and a VO₂Max obtained from CPET. We will be assessing these outcomes in all subjects at baseline and after intervention. Measurements obtained from these exams will evaluate the effect of dapagliflozin treatment on physical indicators of aging.

Cellular Senescence: Senescent cell burden will be assessed in adipose tissue obtained at baseline and after intervention, using both senescence-associated beta-galactosidase staining as well as senescence-associated gene expression assays.

DNA methylation: DNA methylation, a key biological marker of aging, will be evaluated in peripheral blood cells before and after intervention.

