6.1.11. Visit 11 (Week 11-12)

Subjects will arrive fasting to undergo vastus lateralis muscle biopsy, subcutaneous fat biopsy, and collection of blood and urine samples for research purposes. These samples will be used to evaluate treatment effects on tissue cellular senescence, oxidative stress, DNA methylation and mitochondrial function. Post-intervention blood laboratory assays also will be done for CMP, CBC, HbA1c, and lipid panel. Control group subjects will receive nutritional counseling, which may be performed by home visit or a video telehealth visit.

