8.6. Stopping Rules

In the unlikely event that a study-related death or SAE occurs, the decision to stop the trial, either temporarily or permanently, will be the responsibility of the Designated Safety Officer in collaboration with the Principal Investigator.

There are several reasons why the researchers may need to end the subject's participation in the study. Some reasons are:

- 1. The researcher believes that it is not in the subject's best interest to stay in the study
 - Adverse drug reaction that does not resolve by dosing titration or if reaction is severe
 - b. Subject becomes ineligible to participate due to concomitant use of an exclusionary medication
- 2. Subject's health condition changes and needs treatment that is not allowed while participating in the study
- 3. Subject does not follow instructions from the research team.
- 4. The study is stopped

The research team will discuss options for medical care with the subject when participation in the study ends.

9. Data Handling and Record Keeping

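### Subjects taken out of the study under Section 8.6 have no assured Week 11-12 urine or blood sample, because Section 4.4.2 names only survival as the minimum to collect

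*Combined protocol and SAP*

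**What the plan says.** Section 8.6 (Stopping Rules) introduces its list for individual subjects with "There are several reasons why the researchers may need to end the subject's participation in the study". Two of the listed reasons are "Subject becomes ineligible to participate due to concomitant use of an exclusionary medication" and "Subject does not follow instructions from the research team". What ends is study participation; no section describes a subject who is off the intervention but still followed.

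Section 4.4.1 says "Subjects have the right to withdraw fully or partially from the study at any time" but does not say what is collected after a partial withdrawal. It also says that data up to withdrawal of full consent go into the analysis. For subjects withdrawn prematurely, Section 4.4.2 says that "appropriately designated research staff will make efforts to collect at least survival data throughout the protocol defined follow-up period for that subject". It gives survival high priority for those lost to follow-up and refers incomplete data sets to the study statistician.

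Section 3.3 states "The primary endpoint for this study is a reduction in urine AGE-RAGE measurements" and adds "We will be assessing AGE-RAGE in all subjects at baseline and after intervention". The post-baseline sample is taken at Visit 11 (Section 6.1.11): "Subjects will arrive fasting to undergo vastus lateralis muscle biopsy, subcutaneous fat biopsy, and collection of blood and urine samples for research purposes". In the schedule in Section 6.2, research blood and urine appear only at Visits 5 and 11, and there is no early-termination visit.

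Section 7.2 restricts the data to completers, without defining the term. It calls the pilot exploratory and leaves intention-to-treat to a later trial. Section 7.1 says that the data will guide the sample size of future studies.

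**The concern.** The minimum named for withdrawn subjects is a quantity the trial does not study. Over 12 weeks, in subjects selected for good general health, survival will say almost nothing. The one urine sample that carries the primary endpoint is neither required nor scheduled for them.

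The loss may not be random. The excluded drugs in Sections 4.2 and 5.4 include anti-diabetes agents and glucocorticoids, so a subject who starts one may be removed for a reason tied to the biology under study. The instructions to be followed also differ by arm: one tablet a day, against dietary counselling aimed at 3-5% weight loss (Section 3.2). Contact differs too: weekly for controls, less often for the drug arm (Section 6.1.5). Staff apply a discretionary ground knowing the arm.

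At stake is how far the pilot's estimates can serve its stated purpose of informing a later trial, which Section 7.2 says would be analysed by intention to treat. An analysis set can be widened later; a Week 11-12 urine sample that was not taken cannot be recovered.

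**Working it through.** **The text, side by side**

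1. What ends: participation in the study, at the researchers' discretion (8.6).
2. What is then sought: survival, as a floor (4.4.2). Other data are neither named nor forbidden.
3. What the primary endpoint needs: urine at baseline and after intervention (3.3).
4. When that urine is taken: Visits 5 and 11 only (6.2).
5. What covers a subject who leaves between those visits: no sampling visit. Section 8.1 continues adverse-event reporting for 30 days after the last study treatment, but that yields no endpoint sample.

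The post-intervention sample is therefore not assured for withdrawn subjects.

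**Number of subjects**

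The plan derives no sample size or power, so there is no figure to reproduce. The inputs are 20 completers split evenly (3.1) and estimated attrition of 20% (4.3). Assume that all attrition falls after randomisation, which the plan does not state. Then randomised = 20 / (1 - d), rounded up, and missing = randomised - 20.

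| d | Randomised | Without endpoint |
|---|---|---|
| 10% (assumed) | 20/0.90 = 22.2, so 23 | 3 |
| 20% (Section 4.3) | 20/0.80 = 25 | 5 |
| 30% (assumed) | 20/0.70 = 28.6, so 29 | 9 |

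The 5 is an upper bound at the stated rate. The 20% appears in the recruitment and screening section and is not split by cause or timing.

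**Scale of a possible bias (assumed values)**

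Let m be the share missing in one arm and δ the completer mean minus the mean of the missing, in SD units. The all-randomised mean is (1 - m) × completer mean + m × missing mean, so the completer mean differs from it by m × δ. With missing subjects in one arm only:

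| m | δ = 0.25 | δ = 0.5 | δ = 1.0 |
|---|---|---|---|
| 20% | 0.05 | 0.10 | 0.20 |
| 40% | 0.10 | 0.20 | 0.40 |

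The unadjusted standard error of the contrast at 10 per arm is √(2/10) = 0.447 SD. The shifts therefore run from 0.05/0.447 = 0.11 to 0.40/0.447 = 0.89 standard errors. With losses in both arms, the shift in the contrast (drug minus control) is m × δ in the drug arm minus m × δ in the control arm, which can take either sign.

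**The case against.** **The wording is softer than a hard rule.** A reader might infer that non-adherent subjects are always removed, that only survival is collected, and that their samples are never taken. The documents do not support this. Section 8.6 is discretionary, the survival wording in 4.4.2 is a minimum, partial withdrawal is allowed, and nothing prohibits a Visit 11 sample. The ground about instructions sets no adherence threshold. Where weight loss falls short, Section 3.2 offers more counselling; drug compliance is handled by calls and tablet checks (5.2, 5.3, 6.1.6). All of this stands, and it limits the point to samples that are not assured.

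**The size is not known.** A reader might also assume no effect in removed drug-arm subjects and conclude that, at 20% removal, the effect is overstated by 1/0.8 = 1.25 and a later trial undersized by 1.25² = 1.56. The arithmetic is right, but nothing in the documents supports the assumption. The control arm is itself an active weight-loss programme; if poor adherers leave mainly from that arm, the contrast may be understated instead. Bounding analyses would also remain possible, since baseline samples precede assignment. This objection stands.

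**Section 3.3 may only describe timing.** Its sentence about all subjects need not be a promise about those withdrawn. That is a fair reading, but the plan would then be silent on them, which leaves the gap.

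**Completers-only makes it moot.** Section 7.2 discloses that choice, so extra samples might be set aside anyway. This stands only in part: completer is undefined, 4.4.1 points the other way by including data up to withdrawal, and the sample must exist before any analysis set can use it. It does mean that 4.4.2 and 7.2 should be changed together.

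**Conclusion.** The point holds as a gap in data collection. Section 8.6 permits the end of study participation, not only of the intervention. Section 4.4.2 then secures nothing that bears on an endpoint, and no visit fills the gap, so the Week 11-12 urine and blood are not assured for withdrawn subjects.

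At the plan's own attrition figure this touches at most about 5 of 25 randomised subjects, if all attrition follows randomisation (3 of 23 to 9 of 29 for 10% to 30%). How many would be Section 8.6 removals is unknown. That the loss is informative and differs by arm is plausible given the open-label design and the different demands on each arm, but its direction and size are not established. In the illustrations the shift stays below one standard error of a 10-per-arm contrast.

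The change is still worth making: it replaces an uninformative follow-up target with the primary-endpoint sample, at a visit that already exists. No view is taken on when a subject should stop the intervention.

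**What to change.** 1. **Section 4.4.2.** Replace the survival minimum with: at least the Visit 11 fasting urine and blood at Week 11-12 (or at the time of leaving, if the subject will not return), with the subject's consent; biopsies not required. Record the reason and date of withdrawal.
2. **Sections 8.6, 4.4.1 and 4.4.2.** State that stopping the intervention does not by itself end consented sample collection, and reconcile the three sections on this. Leave the clinical grounds in 8.6, and the decision to stop the intervention, as they are.
3. **Section 7.2.** Define completer and reconcile it with the statement in 4.4.1 that data up to withdrawal are included. Alongside the completers analysis, report a supportive analysis of all randomised subjects with a Visit 11 sample, analysed as randomised.

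The cost is an amendment, matching consent wording, and a few extra urine and blood collections. Visit 11 already exists, Section 6.1 allows home visits where safety calls for them, and Section 3.4 covers specimen transport from them. Some subjects will decline, and those who withdraw consent fully or are lost will mostly remain missing. Outcomes that need muscle or fat tissue would not be recovered.

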5.1. Description

The inhibitors of the sodium-glucose co-transporter-2 (SGLT2i) are FDA-approved for the treatment of type 2 diabetes (T2DM). This class of drugs have a unique mechanism of action that involves lowering of plasma glucose concentration secondary to an increase in glucose excretion by the kidney. This glucosuric effect results in a durable reduction in HbA1c, weight loss, improved insulin sensitivity, and enhanced beta cell function (11). Beyond the glucocentric effects of SGLT2i, they have now been shown in patients with cardiovascular disease (CVD) to reduce mortality and hospitalization for heart failure and provide renal protection. These attributes have elevated SGLT2i's to second- or third-line therapy for the treatment of T2DM patients in patients with or without CVD (16-18). Approximately 1/3 of older adults are pre-diabetic. In prediabetes there is limited information regarding the role of SGLT2 inhibitors, but the available data in humans show that prediabetic obese subjects treated with an SGLT2i had significant reductions in weight (19), which is an independent CV risk factor (20) and is associated with insulin resistance, diabetes, dyslipidemia, hypertension, cancer, stroke and nonalcoholic fatty liver disease (21-24). It is likely that the other known glucose and non-glucose lowering effects of SGLT2i could be extrapolated to prediabetic individuals. Dapagliflozin is an SGTL2 inhibitor given for the management and treatment of type 2 diabetes and will be the study drug used for these experiments.

Dapagliflozin (Brand name Farxiga) is administered orally as a yellow pill in either 5mg or 10mg doses. The 10mg dose that will be used in this study is a 4-sided yellow pill with 10 and 1428 printed on opposite sides.

5.2. Treatment Regimen

Administration Protocol.

Following the completion of informed consent, screening visits, enrollment into the study, and baseline measurements, subjects will be provided study drug by the Study Coordinator at the conclusion of Visit 5. Subjects will take 1 pill daily (10mg) as directed during the study period. Subjects will self-administer drug according to product packaging, and compliance calls every two weeks from study investigators will ensure proper scheduling of drug administration as well as to monitor AE development. Subjects randomized to treatment group will receive a 30-day supply of drug during their Visit 5 randomization and will be required to return 4 weeks and 8 weeks later for refilling study drug. **Method for Assigning Subjects to Treatment Groups**

The randomization key will be designed by an objective researcher or statistician not on the study team at the Barshop Institute or from Clinical Research Unit and provided to the Clinical Study Coordinator at the site. The Study Coordinator, as assigned, stores the Enrollment key, which is kept in a locked cabinet. Study staff maintains source documents, data records and specimens in a de-identified manner using only the unique Subject ID/Randomization number.

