Inclusion Criteria	Men and post-menopausal women age 60 and above; BMI 30-38 (BMI 29.5 will be rounded up); diagnosis of pre-diabetes (HbA1c 5.7-6.4%); stable body weight (±3% for ≥3 months); Montreal Cognitive Assessment 21 and above; Subjects must be in good general health as determined by physical exam, medical history, blood chemistries, CBC, TSH, lipid profile, EKG and urinalysis.
Exclusion Criteria	Diagnosis of diabetes based on ADA criteria; impaired renal function with eGFR < 45 mL/min/1.73m²; impaired liver function with labs 3x ULN and above; hematocrit with LLN 30% and below; triglycerides with ULN 600 mg/dL and above; abnormal TSH of 0.3 and below to 10 and above; urinalysis with >5-10 WBC; history of frequent UTI; poorly controlled blood pressure (sysBP >180, diaBP > 100 mmHg); history of recent cardiovascular event in prior 6 months, heart failure, active heart disease; current treatment with drugs known to affect glucose and lipid homeostasis; current treatment with anticoagulants (aspirin <326 mg and clopidogrel permitted if held 7 days prior to biopsies; active inflammatory, autoimmune, gastrointestinal, hepatic, infectious, malignant or uncontrolled psychiatric disease (controlled depression, anxiety, PTSD, etc. enrollment allowed); ; blood donation within 2 months prior to enrollment.
Concomitant Medications	Allowed: Standard of care medications for the management of hypertension, hyperlipidemia and other drugs that at the discretion of the investigator will not interfere with the results of the study. If patient on drugs that affect metabolism like levothyroxine, should be on a stable dose for the last 3 months. Prohibited: Any medications known to adversely affect glucose and lipid metabolism. Additionally, patients on warfarin or other blood thinners except for aspirin up to 325mg and clopidogrel will be excluded.

Study Product, Dose, Route, Regimen	Dapagliflozin, 10mg, Oral, Daily
Duration of administration	12 weeks

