3.2. General Design

This is a single center, open-label, randomized controlled trial. 20 completed subjects are planned. Each subject will be randomized to either the experimental group of dapagliflozin 10mg daily for 12 weeks or the control group of nutritional counseling for weight loss. Healthspan and clinical evaluations will be taken at baseline and at weeks 10-12 of the study.

Screening data will be reviewed to determine subject eligibility. Subjects who meet all inclusion criteria and none of the exclusion criteria will be entered into the study.

The following treatment regimens will be used:

- Dapagliflozin: 10mg per day for 12 weeks. Subjects will return to refill drug medication and perform compliance check at 4 weeks and 8 weeks after beginning treatment.
- Control Group: Subjects will meet with a dietitian every 1-2 weeks throughout the study to discuss nutritional counseling with a goal to lose 3-5% of body weight over 12 weeks to mirror expected SGLT2

inhibitor-derived weight loss over the same period. During these hour-long sessions, volunteers will learn how to adjust their eating habits by following the recommendations of the American Heart Association for reducing dietary fat and substituting complex carbohydrates and reducing energy intake to induce gradual weight loss while maintaining recommended dietary composition. Volunteers also will receive education on portion sizes, meal timing, and meal preparation. Participants receive a notebook of course content and will weigh in prior to each session. Additional counseling visits and/or phone calls may be instituted if desirable weight loss is not achieved. Subjects may be asked to record their dietary intake for a 24-hour period throughout the intervention for review by the dietitian.

Total duration of subject treatment will be 12 weeks. Total duration of the study is expected to be 16-18 weeks.

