6.1.3. Visit 3 (Day -7 to -17 [+/- 2 weeks])

Subjects will come to the Research Imaging Institute for intrahepatic liver fat measurement by Magnetic Resonance Spectroscopy/Imaging.

⁺ Visits 2 and 3 may be performed interchangeably based on DXA and MRI scanner availability.

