6.1.5. Visit 5 (Day 0)

Eligible subjects present to the research unit fasting at appointed time for a vastus lateralis muscle biopsy (39) and subcutaneous fat biopsy (40). We apply local lidocaine for muscle and adipose biopsies. The muscle biopsy is done using a modified Bergstrom technique with suction and the adipose biopsy is done using a mini-liposuction technique. Urine and blood samples also will be collected. These samples will be used for baseline assays of tissue cellular senescence, DNA methylation, oxidative stress and mitochondrial function. After the muscle and adipose tissue biopsies, subjects will be given breakfast and will receive assignment to treatment intervention (randomized) before being discharged to home. Both treatment and control groups will be given a brochure highlighting healthier eating habits. Subjects in the treatment group will be given a 30-day supply of dapagliflozin to begin use the next day. Subjects in the control group will receive a nutritional consultation with a dietician, which may also be conducted by video telehealth visit, with the goal of losing 3-5% body weight during the 3-month period of the study.

- Once intervention phase begins, the study staff will contact subjects assigned to study drug for telephone follow up at Visit 5 +1 week and at or near midpoint between visits to the research unit up to Visit 8.
- Subjects assigned to nutritional counseling group will receive weekly phone calls/video telehealth visits during the intervention phase which will last for 12 weeks.
- Study team members may contact the subjects by phone at any time for AE follow up as needed.

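### Section 5.2 places the randomization key with the Clinical Study Coordinator, and no described step hides upcoming assignments from that role

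*Combined protocol and SAP*

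**What the plan says.** The trial is unblinded: "This is a single center, open-label, randomized controlled trial" (section 3.2).

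Section 5.2 covers allocation in a few sentences. The key is designed by an objective researcher or statistician outside the study team, at the Barshop Institute or "from Clinical Research Unit and provided to the Clinical Study Coordinator at the site". On storage it adds: "The Study Coordinator, as assigned, stores the Enrollment key, which is kept in a locked cabinet". The same section has the Study Coordinator give subjects their drug at the end of Visit 5, and section 6.1.6 allows the study coordinator to conduct Visit 6 as a home visit.

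On timing, section 6.1.5 says that after the muscle and fat biopsies subjects "will receive assignment to treatment intervention (randomized) before being discharged to home".

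On entry, section 3.2 says: "Subjects who meet all inclusion criteria and none of the exclusion criteria will be entered into the study".

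**The concern.** Random allocation protects a comparison in two steps. The sequence must be unpredictable when it is made, and it must stay hidden from those who influence entry until each subject is committed. Section 5.2 secures the first step by using an independent designer. It then passes the key to a site role that deals with subjects, and describes nothing that secures the second.

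If the key can be read ahead, and its holder has any part in recruitment, screening or scheduling, knowing the next arm could affect who reaches Visit 5 and in what order. The arms are easy to tell apart in appeal: a daily tablet against dietitian sessions every one to two weeks (section 3.2). Motivation to diet is a trait on which entry could plausibly be steered. ANCOVA (section 7.2) can adjust for a measured baseline variable that is in the model. It cannot adjust for a trait outside the model.

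**Working it through.** The plan states no figure on this point, so there is nothing to reproduce. The check sets each possible safeguard beside what it does.

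1. **Independent designer (5.2).** This protects how the sequence is generated. It does not limit who can read the sequence after it is handed over.
2. **Locked cabinet (5.2).** The coordinator is its keeper, so it may hide the contents from other staff but not from that role. Section 5.2 also calls the contents the Enrollment key and does not say whether that is the randomization key or a list linking identities to numbers. If they are the same, the keeper holds the sequence. If they differ, no storage rule is stated for the randomization key. Neither reading gives concealment from the coordinator.
3. **Coded Subject ID/Randomization number (5.2).** This protects identity in records and specimens. It is a privacy measure.
4. **Assignment after the biopsies (6.1.5).** This keeps the subject's arm from affecting baseline sampling, provided the arm is not known earlier. It does not hide the arm from a person who already has the list.
5. **REDCap (9.3.1, 9.4).** It is described for data capture, logs and role-based access. No allocation function is mentioned.
6. **Blinding (3.2).** There is none, so blinding cannot stand in for concealment.

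Sealed or numbered envelopes, telephone or web release, and a third party who releases assignments one at a time appear nowhere in the readable text.

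**Size.** The bias would depend on how many entries were steered, on which trait, and on how strongly that trait relates to urine AGE-RAGE, the primary endpoint in section 3.3. The document gives none of these, so no estimate is offered.

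**The case against.** The strongest reply is that harm needs two facts that the document does not supply: that the key is an open list, and that the coordinator consents, screens or schedules. This stands, and it limits the point to an opportunity for bias.

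Existing safeguards also count. Subjects who meet all criteria are to be entered, most criteria are numeric thresholds (4.1, 4.2), the designer is independent, and the trial is exploratory and unpowered (7.2). These reduce both the room for steering and the consequences. They do not conceal the list.

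A reader might infer more than the text supports, in three ways.

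- **Eligibility judgement.** The Study Summary allows "other drugs that at the discretion of the investigator will not interfere with the results of the study" and requires that "Subjects must be in good general health as determined by physical exam, medical history" and other assessments show good health. The discretion named there is the investigator's. Nothing gives the coordinator an eligibility decision or says that the investigator sees the key.
- **Visit windows.** The heading "Visit 3 (Day -7 to -17 [+/- 2 weeks" might suggest that subjects could be reordered. The tolerance applies to Visits 2 and 3, counted back from Day 0. Visit 1 is set at Day -17 to -21 with no such tolerance, so on a literal reading Visit 5 falls 17 to 21 days after Visit 1 wherever the scans land.
- **A numerical bias.** One could calculate how guessable the sequence is, or posit a steered pair of subjects. Both need an assumed list type or assumed correlations. Section 3.1 splits 20 completers evenly, not 20 randomized subjects. Such figures would not measure bias in this trial.

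**Conclusion.** The point holds in a limited form. As written, section 5.2 gives the key to a subject-facing site role, and the document describes nothing that conceals upcoming assignments from that role. This is more than missing detail, because handing over the key is a stated rule and a better arrangement is available at little cost.

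No selection bias is demonstrated and its size is unknown. The conclusion assumes that Clinical Study Coordinator and Study Coordinator name the same role, as the flow of section 5.2 suggests, and that the removed title and contact pages contain no allocation procedure. If a concealment step already exists in practice, the remedy reduces to describing it. Severity is low.

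**What to change.** Amend section 5.2 as follows.

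- The list is not given to the coordinator or to anyone who recruits, screens or schedules subjects.
- The independent statistician either loads it into a REDCap allocation function, if the site has one, or prepares sequentially numbered, opaque, sealed envelopes. An existing role that does not enrol holds the envelopes. The Research Drug Manager is a candidate: the duties in section 5.6 concern the drug supply only.
- Each assignment is released only after eligibility and Visit 5 baseline sampling are recorded. Section 9.3.1 already allows time-stamped eligibility records in REDCap.
- Any block sizes are kept from site staff, since past assignments are visible in an open-label trial.
- The text states whether the Enrollment key is the randomization key.

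The cost is one paragraph and a small set-up task, with no added visits or subjects. If all of the estimated 20% attrition (section 4.3) followed assignment, 20 / (1 − 0.20) = 25 assignments would be needed, or 26 for a list with equal arms; fewer if some attrition comes earlier. The downside is that the envelope holder must be reachable at each Visit 5. The change cannot protect assignments already made.
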